7.3.2 Analysis of secondary endpoints

For the secondary outcome of cumulative medication prescribing, we will use an identity link function and normally distributed errors within the generalized linear models. For tertiary adverse clinical outcomes and resource utilization outcomes, we will use a log link function and binary distributed errors. These models generate the estimated relative risks (RRs) with robust standard errors and are considered to be particularly appropriate when outcomes are common (e.g., incidences of $\geq 10\%$). For these outcomes from claims data, we will follow patients whose providers are randomized to the study from the time of randomization until they are censored due to loss of continuous enrollment in their health plan. Due to the nature of the randomization, we do not anticipate any systematic differences in the amount of follow-up time per arm but will account for any imbalances using inverse probability censoring weights.

Because this is a randomized trial, our primary analyses are planned as unadjusted; however, if there are strong patient-level predictors of the outcomes not balanced by stratified randomization, we will adjust for these. Given the nature of the data and how the outcomes are being measured, there should not be missing values. However, should there be sufficient missing data (e.g., $> 10\%$), we will use multiple imputation.²⁵

7.3.3 *Baseline descriptive analyses*

We will report the means and frequencies of pre-randomization variables separately for intervention and control subjects. Comparisons of these values will be performed using t-tests and chi square tests and their non-parametric analogs, as appropriate. The outcomes will be evaluated using intention-to-treat principles among all randomized patients.

7.3.4 *Subgroup analyses*

In subgroup analyses, we will explore whether there were any modifiers of the effects of the EHR tools. For example, we will explore if certain types of providers (e.g., by specialty) were more likely to respond to the EHR tools or if there were observable differences in patients who were less likely to receive inappropriate medications, such as gender or race/ethnicity.

7.3.5 *Exploratory analyses*

In secondary analyses, we will control for potential confounders which will be measured using EHR data from structured fields and administrative claims data. These variables will include provider characteristics (such as specialty, age, and gender), patient characteristics (such as major comorbidities, race/ethnicity, and age), and practice characteristics (such as practice size).

8. Ethical and regulatory requirements

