3.2 Overall design

We will conduct a parallel group trial at Mass General Brigham, specifically within MGH primary care practices. We hypothesize that these tools will reduce prescribing of high-risk medications (primary outcome), cumulative prescribing of high-risk medications (secondary outcome), and clinically-significant adverse drug events like sedation and confusion (tertiary outcome) compared with usual care.

3.2.1 *Trial Design*

[figure not shown]
This trial is a cluster-randomized, NIH-defined Phase III pragmatic trial. The study statistician, in partnership with data analysts at MGB, will generate and implement the randomization scheme, with oversight by the Principal Investigators. All the study sites will be at MGH for this trial; we have received approval from leadership at MGH primary care practices and Digital Health eCare teams to conduct this trial. For study evaluation, data regarding patients' medical history, disease control, medication use, and healthcare utilization will be obtained from EHR data or administrative claims data. Any administrative claims data used for evaluation in this study will come directly from MGB in HIPAA-limited datasets through their risk-bearing contracts.

We will randomize primary care providers at MGH to one of the 2 most promising treatment arms identified in the prior adaptive randomized trial conducted at Atrius Health or usual care (described in further detail in 5.2). We expect to randomize approximately 200 providers. Providers randomized to one of the 2 selected treatment arms will receive an EHR tool to guide their care of eligible patients. We will randomize providers based on provider demographic characteristics, patient case-mix factors, and baseline rates of high-risk medication prescribing measured in EHR data.

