4.1 Inclusion Criteria

The subjects involved in this trial are providers from multiple clinical sites, all at Mass General Hospital. The target population of providers and the patients they treat is pragmatic and widely representative. Providers will be eligible if they treat older adult patients. Each study clinic has an EHR system in place. The inclusion criteria are limited to maximize generalizability in accordance with pragmatic trial principles by PRECIS-2 (PRagmatic Explanatory Continuum Indicator Summary).

Providers will be eligible if they:

- Are a primary care provider at Mass General Hospital, with a minimum clinical schedule of 2 sessions per week
- Prescribed a benzodiazepine, sedative hypnotic, or anticholinergic to at least one older adult in the 180 days prior to randomization

Patients will be included in the analysis if they:

- Are assigned to one of the randomized primary care providers (by MGB indicators)
- Are aged 65 years or more
- Have been prescribed at least 90 pills of benzodiazepine or sedative hypnotic or at least one active orders of at least 90 pills of two different anticholinergics in the prior 180 days

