5.3 Measures to minimize bias: randomization and blinding

Providers will be randomized to treatment arms in equal proportions based on blocks. We will use provider-based cluster randomization to minimize the possibility of contamination in study interventions between practices and clinic staff. For the randomization, we will use stratified randomization based on clinic practice size and baseline rates of prescribing to reduce potential imbalances between the providers assigned to the treatment arms.

The providers will not be blinded to which arm they were assigned to, as blinding is the context of an intervention that is intended to motivate action will be infeasible. The study

analyst will generate and implement the randomization scheme, with oversight by the Principal Investigators. Investigators will be blinded to the treatment arms during interim and final analyses.

6. Study Assessments and Procedures

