6.1 Baseline data

We will collect baseline data on patients and providers using extracted EHR data and/or administrative claims data as applicable for the study aim. This baseline data will be used to assess any potential imbalances in the characteristics of providers or patients despite randomization. The baseline data will include, but are not limited to: gender, baseline rates of prescribing, practice location, and patient case-mix. We will also collect patient data that include but are not limited to: sociodemographic data, medical history and comorbidities, baseline resource utilization in prior 12 months (i.e., number of visits), biometric values (e.g., serum creatinine, systolic/diastolic blood pressures).

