6.2 Outcomes

The primary outcome will be a binary composite measure of a reduction in inappropriate prescribing, evaluated using EHR data. In specific, we will measure a composite of 1) discontinuation of high-risk medications (benzodiazepines, sedative hypnotics, or anticholinergics) defined by either: a) active discontinuation and no subsequent order or b) no order during follow-up or 2) ordering a gradual dose taper (for benzodiazepine or sedative hypnotics). Our primary analyses will be within patients who had a visit (telemedicine or in-person) with a study provider after randomization. If either of these actions is taken by providers for a specific patient at any point in the follow-up window, we will classify the patient as having had a reduction in inappropriate prescribing. If the patient has multiple therapeutic classes of interest (e.g., benzodiazepines and sedative hypnotics), we will classify patients with a reduction for any class as a “reduction” for the composite measure. We will also stratify

patients by their number of eligible therapeutic classes (i.e., one, two, or three classes) and analyze outcomes within these strata.

Secondary outcomes include the quantity of high-risk medication prescribed, defined by number of pills of high-risk medications (all three classes) prescribed to patients in the follow-up period and number of lorazepam milligram equivalents of benzodiazepines and sedative hypnotics to capture cumulative prescribing by all providers. As above, we will also stratify patients by their number of eligible therapeutic classes (i.e., one, two, or three classes) and analyze outcomes within these strata.

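### The main analysis of the two secondary quantity outcomes omits the patient's prior quantity and the randomisation strata, and an undefined imbalance rule leaves the model open; precision is likely lost, by an amount the documents cannot fix

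*Combined protocol and SAP*

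**What the plan says.** Section 6.2 defines two secondary quantity outcomes over follow-up: pills across all three drug classes, and "number of lorazepam milligram equivalents of benzodiazepines and sedative hypnotics". Section 7.3.2 gives cumulative prescribing a linear model (identity link, normal errors), with no covariates by default. It then qualifies this: "if there are strong patient-level predictors of the outcomes not balanced by stratified randomization, we will adjust for these".

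Other sections bear on the point:

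- Section 7.3.3 plans baseline tests by arm ("Comparisons of these values will be performed using t-tests and chi square tests") but does not connect them to the adjustment rule.
- Section 3.2.1 says the trial will "randomize providers based on provider demographic characteristics, patient case-mix factors, and baseline rates of high-risk medication prescribing". Section 5.3 instead describes "stratified randomization based on clinic practice size and baseline rates of prescribing". Only baseline prescribing appears in both lists.
- Section 6.1 says the baseline data will "include, but are not limited to: gender, baseline rates of prescribing, practice location, and patient case-mix", for the purpose of assessing imbalance.
- Section 7.3.5 allows secondary analyses with an illustrative list of provider, patient and practice characteristics. Practice size is named; the patient's own baseline quantity is not.
- Section 4.1 makes eligibility depend on prior prescribing of the same classes: at least 90 pills of a benzodiazepine or sedative hypnotic, or "at least one active orders of at least 90 pills of two different anticholinergics in the prior 180 days".

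For the primary endpoint, by contrast, section 7.3.1 states an unadjusted main analysis and a closed covariate list (age, race/ethnicity, gender) for the secondary one.

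**The concern.** Two things are left open.

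First, the choice of model. Two analysts could follow section 7.3.2 faithfully, disagree on what counts as a strong predictor or an imbalance, and report different main results. Each would have chosen after seeing baseline data by arm.

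Second, precision. The outcome is later prescribing of the drugs that made the patient eligible, so the patient's earlier quantity is the natural covariate. Adjustment gains precision because a covariate predicts the outcome, whether or not the arms look unbalanced, so an imbalance trigger is a poor substitute for naming it. In addition, a robust standard error from a model without the strata takes no credit for variance that stratified allocation has already removed.

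At stake is the width of the intervals on the trial's only secondary outcomes. The plan states no power, standard deviation or target effect for them.

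**Working it through.** **Inputs from the documents.** About 200 providers in three equal arms (sections 3.2.1 and 5.3): 200/3 is about 66 per arm, so 132 in each arm-versus-usual-care contrast. The intra-provider correlation (ICC) of 0.1 in section 7.2 is stated for the primary outcome and borrowed here. Eligibility sets a 90-pill floor (section 4.1). There is no stated precision figure for these outcomes to reproduce.

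**Assumptions.** Patients per provider m = 10 or 20. Patient-level baseline-to-follow-up correlation rw = 0.3, 0.5 or 0.7. Provider-level correlation rb equal to rw, half of it, or zero.

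**Step 1: why the provider level matters.** With unit variances, the variance of a provider mean is ICC + (1 − ICC)/m.

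- m = 10: 0.1 + 0.9/10 = 0.19, of which the provider part is 0.1/0.19 = 53%.
- m = 20: 0.1 + 0.9/20 = 0.145, of which the provider part is 0.1/0.145 = 69%.

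One baseline slope fitted under working independence is b = ICC·rb + (1 − ICC)·rw. The residual variance of a provider mean is then

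ICC(1 − 2b·rb + b²) + (1 − ICC)(1 − 2b·rw + b²)/m.

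For rw = 0.5 and m = 20:

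- rb = 0.5: b = 0.5, and the standard-error ratio is √(1 − 0.25) = 0.866, a fall of 13%.
- rb = 0.25: b = 0.475. Variance 0.1 × 0.9881 + 0.9 × 0.7506/20 = 0.1326. Ratio √(0.1326/0.145) = 0.956, a fall of 4%.
- rb = 0: b = 0.45. Variance 0.1 × 1.2025 + 0.9 × 0.7525/20 = 0.1541. Ratio √(0.1541/0.145) = 1.031, a rise of 3%.

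If the provider mean of baseline is a second term, the rb = 0 case becomes √[(0.1 + 0.9 × 0.75/20)/0.145] = √(0.13375/0.145) = 0.960, a fall of 4% instead of a rise.

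**Step 2: closer to the real outcomes.** Step 1 assumes plain normal data. The simulated quantities are log-normal (log SD 0.7, untruncated median 180), with baseline truncated below at 90 pills and 25% zero follow-up totals independent of baseline. Correlations apply on the log scale before the floor and zeros. For lorazepam equivalents, an assumed 20% of patients qualify on anticholinergics alone and are zero at both times; one strength per pill is assumed for everyone. Analysis is a linear model with cluster-robust standard errors. Change in the reported standard error from adding baseline quantity:

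| Outcome | Provider-level correlation | rw = 0.3 | rw = 0.5 | rw = 0.7 |
|---|---|---|---|---|
| Pills | equal | falls 1-2% | falls 4-6% | falls 12-14% |
| Pills | half | falls 0-1% | falls 1-2% | falls 3-5% |
| Pills | zero, m = 10 | no change | no change | no change |
| Pills | zero, m = 20 | rises about 1% | rises about 2% | rises about 4% |
| Lorazepam equivalents | equal | falls 4-5% | falls 9-10% | falls 17% |
| Lorazepam equivalents | half | falls 2-3% | falls 4-6% | falls 6-10% |

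**Step 3: the strata.** If providers were stratified by tercile of their mean quantity, an optimistic case, the true sampling variance for pills would fall by only 0-1%, 2-3% and 5-7% at equal correlations, because the design has already taken most of the gain. The unadjusted standard error does not show this. In a plain normal simulation at correlation 0.7 (m = 10, stratified on provider baseline level):

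- Unadjusted: reported standard error 0.0754 against a true 0.0670, so 0.0754/0.0670 = 1.125, or 12.5% too large; type I error 2.4% against a nominal 5%.
- Strata added: 0.0667 reported against 0.0670 true. The estimate is no more precise, but its standard error is now right.
- Strata and baseline added: 0.0534 reported against 0.0545 true; type I error 5.5%.

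With normal critical values the strata-plus-baseline model ran at 4.7-6.7% across settings. A degrees-of-freedom factor with t critical values brought it to 4.1-5.4%.

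**The case against.** The best defence has four parts.

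**The default is stated.** Section 7.3.2 can be read as keeping the unadjusted analysis as the main one, with adjustment as a supplement, as in section 7.3.1. That reading is tenable. It settles the model choice but leaves the main intervals unadjusted, so the precision point remains. A reader might infer that the section 7.3.3 tests decide which model is reported. The documents do not link the two, so no switching rate can be attributed to the plan.

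**The gain is not guaranteed.** This stands. A reader might infer that the intervals are certainly wider than needed, or take √(1 − r²) at face value. Neither is supported: the documents give no correlation at either level, the outcomes have a floor and zeros, and at low provider-level correlation the gain for pills disappears or reverses. The lorazepam rows also rest on an assumed anticholinergic-only share.

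**Stratification already handles part of it.** This also stands, to the extent that the strata track quantity. What then remains is mainly a standard error that is too large.

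**Unadjusted analysis is legitimate.** It is. A reader might infer bias or false-positive inflation from the missing covariates; randomisation rules out the first, and where stratification works the error runs in the conservative direction. The open-ended lists in sections 6.1 and 7.3.5 would permit the missing terms, but they do not commit to them.

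**Conclusion.** The point holds as one of pre-specification and likely precision. The imbalance rule is undefined, its effect on the main analysis is unstated, and the main model names neither the prior quantity nor the strata. The size is conditional: for pills, from a 12-14% lower reported standard error (correlation 0.7 at both levels) to nothing or a rise of up to 4% (no provider-level correlation); for lorazepam equivalents, 2-17% lower over the equal and half cases examined. All of this rests on assumed correlations, cluster sizes, zero fractions and distributions, and on an ICC borrowed from the primary outcome. Where stratification closely tracks provider mean quantity, the true variance gain for pills is about 0-7%, and at high correlations the unadjusted standard error tends to be conservative. The change is worth making because it closes an open choice at low cost, but it is not a validity defect.

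**What to change.** For the two quantity outcomes only, pre-specify one main model giving both arm-versus-usual-care contrasts, with these terms:

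- arm;
- the patient's quantity in the 180 days before randomisation, in the outcome's own unit (all-class pills, or lorazepam milligram equivalents);
- the stratification factors actually used, once sections 3.2.1 and 5.3 have been reconciled.

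Keep provider clustering and robust standard errors, and add a small-sample correction. The provider mean of baseline quantity is an optional further term that guards against loss when provider-level correlation is low. Number of eligible classes is also optional: section 6.2 already plans analyses within those groups, and its contribution to precision was not assessed. Report the unadjusted difference as a sensitivity analysis, and state that the imbalance rule does not apply to these outcomes.

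The cost is SAP wording plus programming to derive the two baseline totals from EHR orders already searched for eligibility. Eligibility needs only a threshold, so the totals may not yet exist, but no new data source is needed. The downside is that precision may improve little or not at all if provider-level correlation is low.

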7.3 Statistical analyses

7.3.1 *Analysis of the primary endpoints*

The unit of analysis is at the patient-level. All analyses will use intention-to-treat principles. We will use generalized estimating equations to adjust for clustering and repeated observations per provider to evaluate the effectiveness of the intervention arms versus usual care. For the inappropriate prescribing outcome, we will use a log link function and binary distributed errors. These models generate the estimated relative risks (RRs) with robust standard errors and are considered to be particularly appropriate when outcomes are common (e.g., incidences of $\geq 10\%$). Because this is a randomized trial, our primary analyses are

planned as unadjusted; however, in secondary analyses, we will adjust for patient age, race/ethnicity, and gender.

Given the nature of the data and how the outcomes are categorized, there will not be missing values for the primary endpoint, as the absence of action is classified as no action by the provider. For the primary analysis, we will include all eligible patients in the denominator who had at least one visit with their primary care provider. In secondary analyses, we will include all eligible patients of those primary care providers in the denominator, regardless of whether the patient visited the provider over the follow-up period.

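### Section 7.3.3 tests patient-level baseline variables with methods that ignore randomisation by provider, so those p-values are somewhat too small; separately, 7.3.2 ties covariate adjustment to an imbalance it does not define

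*Combined protocol and SAP*

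**What the plan says.** The unit of randomisation is the provider. Section 3.2.1 calls the trial cluster-randomised and expects about 200 providers. Section 5.3 says: "We will use provider-based cluster randomization to minimize the possibility of contamination".

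Section 6.1 collects baseline data at both levels. On patients: "We will also collect patient data that include but are not limited to: sociodemographic data, medical history and comorbidities". On purpose: "This baseline data will be used to assess any potential imbalances in the characteristics of providers or patients despite randomization".

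Section 7.3.3 sets out the baseline table: "We will report the means and frequencies of pre-randomization variables separately for intervention and control subjects". The next sentence gives the method: "Comparisons of these values will be performed using t-tests and chi square tests and their non-parametric analogs, as appropriate". No allowance for clustering is mentioned.

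Clustering is handled in section 7.3.1: "We will use generalized estimating equations to adjust for clustering and repeated observations per provider". That sentence goes on to limit itself to evaluating the effectiveness of the arms.

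Section 7.3.2 keeps the main secondary and tertiary analyses unadjusted, with one exception: "if there are strong patient-level predictors of the outcomes not balanced by stratified randomization, we will adjust for these". Section 7.3.5 lists possible confounders by example, including "patient characteristics (such as major comorbidities, race/ethnicity, and age), and practice characteristics (such as practice size".

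**The concern.** Patients of one provider tend to resemble one another, and they are allocated together. A t-test or chi-square test on individual patients treats them as independently allocated and so understates the standard error of the difference between arms. The p-value is then too small as an answer to the question of whether the difference is larger than this randomisation would produce by chance. The plan allows for clustering in its power statement and its effectiveness models, but not in the one place where it says how patient balance will be compared.

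A second, separate matter is the adjustment rule in 7.3.2. It depends on predictors being unbalanced but does not say how imbalance is judged, and the lists in 7.3.5 are open. The covariates of adjusted secondary and tertiary models can therefore be settled after the data are seen.

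The stakes are modest: a baseline table whose p-values mislead, and some analyst freedom in adjusted models that are not the main analyses.

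**Working it through.** **1. The plan's own figure.** The documents state no error rate for the baseline tests. The nearest figure is the power claim in 7.2: more than 80% for a 10-point difference from 25%, intra-provider correlation 0.1. It cannot be reproduced, because patients per provider (m) is not given, but it shows what m it would need. Assume two-sided alpha 0.05 (not stated) and 200/3 = 66.7 providers per arm, from equal allocation to three arms.

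- Effective patients per arm, 25% v 35%, 80% power: [z × √(2 × 0.30 × 0.70) + 0.842 × √(0.25 × 0.75 + 0.35 × 0.65)]² / 0.10². This gives 329 at alpha 0.05 (z = 1.960) and 398 at alpha 0.025 (z = 2.241, Bonferroni for two comparisons).
- Setting 66.7m / (1 + 0.1(m − 1)) equal to n gives m = 0.9n / (66.7 − 0.1n). This is 8.8, so 9 patients, for n = 329, and 13.3, so 14 patients, for n = 398.

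Panels of 5 to 14 are therefore a reasonable range to examine. Actual panels may differ.

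**2. Error rate of an ordinary patient-level test.** With equal panels, the design effect is DE = 1 + (m − 1) × ICC. The ordinary standard error is too small by the factor 1/√DE, and the true two-sided error of a nominal 5% test is 2Φ(−1.96/√DE). The ICC here belongs to the baseline variable. The documents give none, so 0.01 to 0.05 is assumed.

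| m | ICC | DE | 1.96/√DE | True error | SE understated by |
|---|---|---|---|---|---|
| 5 | 0.01 | 1.04 | 1.922 | 5.5% | 1.9% |
| 10 | 0.01 | 1.09 | 1.877 | 6.0% | 4.2% |
| 14 | 0.02 | 1.26 | 1.746 | 8.1% | 10.9% |
| 10 | 0.05 | 1.45 | 1.628 | 10.4% | 17.0% |
| 14 | 0.05 | 1.65 | 1.526 | 12.7% | 22.2% |

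Among 10 patient variables (an assumed number) with no systematic difference, the expected number of flags per two-group comparison is 10 × the true error: about 0.55 to 1.27, against 0.50 nominally.

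**3. Check by simulation.** With no true difference, 67 providers per arm, equal panels and 4,000 runs per setting, the patient-level t-test rejected in 5.4% of runs (m = 5, ICC 0.01), 5.9% (10, 0.01) and 9.6% (10, 0.05), close to the formula. A t-test on provider means rejected in 4.2% to 5.7% over all settings tried (m = 5, 10 and 20; ICC 0 to 0.1). Respecting the cluster therefore restores the nominal level.

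**4. What pushes the figure up or down.** Unequal panels raise it: with panel sizes drawn from a gamma-Poisson distribution (gamma coefficient of variation 0.6, assumed), simulation gave about 7% at mean m = 10, ICC 0.01 and about 16% at mean m = 14, ICC 0.05. Stratification on practice size and baseline prescribing (5.3) lowers it for variables tied to those factors; this was not modelled. At ICC 0 there is no excess.

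**5. Where it does not reach.** A provider-level variable has one value per randomised unit, so ordinary tests are not inflated by clustering. The primary analysis is an unadjusted GEE that accounts for clustering by provider and uses no baseline test.

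**The case against.** The best defence has four parts.

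- **The table itself is right.** A reader might infer that it would overstate the imbalance. The documents do not support that. The arm means and frequencies show the differences that actually arose; randomising clusters simply produces larger chance differences between patients, with a standard deviation √1.65 = 1.28 times as large at m = 14, ICC 0.05. Only the p-value is miscalibrated. This stands.
- **The open covariate choice has another cause.** A reader might infer that inflated p-values will pick the covariates in 7.3.2. Nothing says so. The rule also requires a strong predictor of the outcome, which a small baseline p-value alone does not show. The freedom comes from the missing criterion in 7.3.2 and the open lists in 7.3.5, and would remain with perfectly calibrated tests. This stands, so the two matters are kept apart here. Nor would adjusting for a strong predictor in itself bias the comparison.
- **The patient-level reading is partly inferred.** Section 7.3.3 is descriptive, attaches no decision to the tests and speaks of subjects, a word the protocol uses for both providers and patients. But 6.1 collects patient variables expressly to assess balance, and 7.3.3 itself goes on to refer to randomised patients. The inference is sound.
- **The size is assumed and may be trivial.** True at the low end. It is also tempting to apply the plan's correlation of 0.1, which would give 15.5% at m = 10 and 19.6% at m = 14. That value is stated for the primary outcome, and the documents do not support carrying it over to baseline characteristics.

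None of this makes an unclustered test right for patient variables, and none of it supplies the criterion missing from 7.3.2.

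**Conclusion.** As written, 7.3.3 specifies the wrong reference distribution for patient-level baseline comparisons. The true error of a nominal 5% test is about 5.5% to 12.7%, given the panel sizes, equal panels and correlations assumed above; the documents supply none of these. At the lower end the excess does not matter in practice.

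The rule in 7.3.2 is a distinct and equally modest weakness: adjustment depends on an undefined finding of imbalance. A reader might take the two together as a threat to the trial's main conclusion. The documents do not support that, because the main analyses are planned as unadjusted and the primary one already accounts for clustering. Low priority, but worth correcting because a stated method does not fit the design.

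**What to change.** **Section 7.3.3.** Describe patient-level variables with standardised differences and drop the ordinary tests; if tests are kept, cluster them on provider. State that baseline p-values will not be used to select covariates. Ordinary tests may stay for provider-level variables.

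**Section 7.3.2.** Replace the imbalance-triggered adjustment with a prespecified set. One option is the age, race/ethnicity and gender already named in 7.3.1, plus any specific variables from 7.3.5, each listed by name before the investigators are unblinded to arm. Category labels such as major comorbidities or provider characteristics would leave the set open, so the individual variables need naming. Keep the unadjusted analysis as the main one.

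**Cost.** Wording only: no new data and no change to the primary analysis. The small price is giving up adjustment for an unforeseen imbalance in a variable outside the named set.
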